## 11. Statistical Analysis

- **General consideration:** The primary analysis will be conducted on ITT basis. Analysis of covariance (ANCOVA) with complete data will be the primary analysis for efficacy. Multiple imputation will apply because of missing data and sensitivity analysis will be conducted in various ways, including linear mixed effects model and pattern-mixture model approach. Compliance of intervention will be summarized using the number of pills taken as the proportion of planned number of pills. The association of compliance with each of the outcomes ( $FMD_{BA}$  aPWV and LVMI) will be explored using multiple linear regression. Participants who receive rescue therapy will be analyzed in the ITT analysis but excluded from the per-protocol analysis. We will also analyze the data with and without adjustment for change in eGFR, exploring its potential effect. All analyses will be performed using SAS version 9.4 (SAS Institute, Cary, NC, USA).
- **Descriptive statistics:** Descriptive statistics of baseline characteristics and outcomes variables will be provided for all enrolled participants; mean and standard deviation for continuous variable and proportion for categorical variable. Summaries will be provided for the full cohort and for subgroups defined by age, gender, and baseline kidney function. Highly-skewed variables may be transformed prior to statistical analyses to better approximate normality. Change over time in outcome variables will be presented by using appropriate charts and tables.
- **Analysis Plan for Aim 1:** The goal of this aim is to compare changes from baseline to 12 months in  $FMD_{BA}$  and aPWV between the two groups and ANCOVA will be used to test the difference. In all analyses, a  $p \leq 0.025$  will be considered significant. Furthermore, we will investigate how  $FMD_{BA}$  and aPWV change over time in one year by using longitudinal data analysis with mixed effect models. We will perform analysis of response profile in which we will assess the mean level of  $FMD_{BA}$  and aPWV at all time points in each group and examine for differences between groups at each time point. In addition, will assess for an effect of the intervention vs. placebo prior to the end of study. We will also fit parametric curves if exploratory analyses find a curve pattern of change over time in  $FMD_{BA}$  and aPWV.
- **Analysis Plan for Aim 2:** The goal of this aim is to compare changes from baseline to 12 months in LVMI between the two groups and ANCOVA will be used to test the difference. In all analyses, a  $p \leq 0.05$  will be considered significant.
- **Analysis Plan for Aim 3:** The goal of this aim is to compare changes from baseline to 12 months in plasma levels of All, aldosterone and ET-1 and serum levels of  $T_{50}$  between the two groups and ANCOVA will be used to test the difference. In all analyses, a  $p \leq 0.05$  will be considered significant.

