## 10. Power Calculations

**a) Aim 1:** Effect sizes were estimated for the primary endpoints of  $FMD_{BA}$  and aPWV based on published data of a similar population. We hypothesize that participants randomized to the bicarbonate group will have an improvement (i.e., increase) in  $FMD_{BA}$  at 12 months, while those in placebo will have a decrease in  $FMD_{BA}$ . We will compare change (from baseline to 12 months) in  $FMD_{BA}$  between the two groups. A previous study of paricalcitol vs. placebo in CKD stage 3-4 showed a between group difference of 1.8% in changed  $FMD_{BA}$  with 95% CI 0.3-3.1% after 12 weeks. Our preliminary data showed a between group difference (bicarbonate vs. control) of 1.6% in changed  $FMD_{BA}$  with 95% CI 0.2-2.9% after 6 weeks. Assuming a standard deviation of change of 0.8%, 54 patients in the placebo group and 54 patients in the bicarbonate group achieves 99% power to detect a 1.5% difference among the means (which is a clinically meaningful difference) using the two sample t-test with a two-sided 0.025 significance level (i.e. 5% significance level after Bonferroni correction for 2 outcomes) for intent-to-treat (ITT) analysis. It would also achieve 99% power to detect the same effect size in per-protocol analysis (n=45 per group allowing for 15% attrition). We hypothesize that participants randomized to the bicarbonate group will have no change or a decrease in arterial stiffness measured by aPWV at 12 months, while those in placebo will have an increase in stiffness. We will compare change (from baseline to 12 months) in aPWV between the two groups. In previous studies of CKD patients with comparable kidney function, the mean (SD) increase in aPWV was  $1.1 \pm 1$  m/s over a 12 month period. Assuming a common standard deviation within a group of 1.5 m/s, 54 patients in each group will provide 88% power to detect a 1.0 m/s difference among the means (which is a clinically significant difference) using the two sample t-test with a two-sided 0.025 significance level (i.e. 5% significance level after Bonferroni correction for 2 outcomes) for ITT analysis. It would also achieve 80% power to detect the same effect size in per-protocol analysis (n=45 per group allowing for 15% attrition).

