**b) Aim 2:** Effect sizes were estimated for the outcome of LVMI (normalized to height to the 2.7th power) based on published data of longitudinal changes in LVMI. We hypothesize that participants randomized to the bicarbonate group will have a decrease in LVMI at 12 months whereas those in placebo will have no change or an increase in LVMI. We consider 5-g of between-group difference in absolute LV mass as clinically important based on previous studies where 10-g was considered for 2 years study duration, implying a mean between group-difference of 1.2 in LVMI, given mean height of 1.70 m. We further estimate the SD of the change in LVMI to be 1.8 based on information provided in the same study. Hence, 54 patients in each group will provide 93% power to detect a significant 5-g difference in absolute LV mass or a 1.2 g/m2.7 difference in LVMI between the two groups at 12 months using a two sample t-test with a 0.05 significance level.

**c) Aim 3:** We hypothesize that participants randomized to the bicarbonate group will have a decrease in plasma All, aldosterone and ET-1 12 months whereas those in placebo will have no change or an increase. Based on data from a small trial of alkali therapy in participants with CKD, we expect the mean ET-1 level to decrease by 0.9 pg/mL with a SD of 0.4 pg/mL and the mean aldosterone level to decrease by 20 pg/mL with a SD of 10.1 pg/mL from baseline to 12 months in the bicarbonate group. The planned sample size of 54 patients in each group will provide >95% power to detect the difference between the two groups. Based on published data in hypertensive patients with normal renal function, we expect the mean All level to decrease by 30% from baseline to 12 months in the bicarbonate group. The planned sample size of 54 patients in each group will provide >95% power to detect the difference between groups. There is very limited data regarding change in  $T_{50}$  levels in CKD patients. We hypothesize that the bicarbonate group will have an increase in  $T_{50}$  whereas the placebo will not change or decrease. Based on published data in CKD stage 3-4 patients, we expect the

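### The stated powers for aPWV, LVMI and T50 fit the complete-data primary analysis only if all 54 per arm have a month-12 value (minor)

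*Combined protocol and SAP*

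**What the plan says.** Section 11 (General consideration) sets an ITT basis for the primary analysis and then states: "Analysis of covariance (ANCOVA) with complete data will be the primary analysis for efficacy". The next sentence reads: "Multiple imputation will apply because of missing data and sensitivity analysis will be conducted in various ways", and goes on to list a linear mixed model and a pattern-mixture model. On populations it says: "Participants who receive rescue therapy will be analyzed in the ITT analysis but excluded from the per-protocol analysis".

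Section 10 bases power on a two-sample t-test of the change from baseline to month 12.

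- **aPWV (Aim 1, two-sided 0.025, labelled ITT):** "Assuming a common standard deviation within a group of 1.5 m/s", "54 patients in each group will provide 88% power to detect a 1.0 m/s difference among the means". The same paragraph adds "80% power to detect the same effect size in per-protocol analysis (n=45 per group allowing for 15% attrition".
- **FMD (Aim 1):** 99% power at 54 per arm, and 99% at the same per-protocol n of 45.
- **LVMI (Aim 2, 0.05):** "54 patients in each group will provide 93% power to detect a significant 5-g difference in absolute LV mass", with a difference of 1.2 and an SD of change of 1.8.
- **T50 (Aim 3, two-sided 0.05):** 95% power at 54 per arm for an effect size of 0.7.

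Aims 2 and 3 make no allowance for attrition.

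**The concern.** A complete-data ANCOVA of 12-month change can use only participants with a month-12 value. The plan expects to lose some, yet its headline powers take 54 per arm, which is everyone randomised. The 15% allowance is applied only to the per-protocol set. If it means loss of the outcome, the same loss shrinks the complete-data ITT set.

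At stake is whether readers are told the power of the analysis that the plan calls primary. A smaller matter is that section 11 says imputation will apply without giving its role. With missing month-12 data, complete-case and imputed analyses can give different estimates and p-values for the two primary outcomes, so their ranking should be explicit.

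**Working it through.** **Inputs (section 10).** aPWV: difference 1.0 m/s, SD 1.5, two-sided α 0.025. LVMI: difference 1.2, SD 1.8, α 0.05 (taken as two-sided; Aim 2 does not say). T50: effect size 0.7, two-sided α 0.05. Allocation is 1:1 with 54 per arm, and attrition is 15%.

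**Formula.** Two-sample t-test: δ = d·√(n/2) with d = difference/SD, df = 2n − 2. Power = P(T > t(1 − α/2, df)), where T is noncentral t with noncentrality δ; the other tail is negligible.

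**Step 1: reproduce the plan at n = 54.**
- aPWV: d = 1/1.5 = 0.667, δ = 0.667 × √27 = 3.46, power 88.1% (stated 88%).
- LVMI: d = 1.2/1.8 = 0.667, δ = 3.46, power 93.0% (stated 93%).
- T50: d = 0.7, δ = 3.64, power 95.0% (stated 95%).

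All three match, and each needs 54 observed values per arm.

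**Step 2: apply the plan's own attrition.** 54 × 0.85 = 45.9, so 46 per arm. The plan itself uses 45. The documents do not define attrition; the 46 and 45 columns assume that all of it means no month-12 value. The 50 column shows the case where about half of those counted still attend.

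| Outcome | n = 54 | n = 50 | n = 46 | n = 45 |
|---|---|---|---|---|
| aPWV | 88.1% | 85.3% | 81.9% | 80.9% |
| LVMI | 93.0% | 91.0% | 88.6% | 87.9% |
| T50 | 95.0% | 93.4% | 91.3% | 90.7% |

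At 46 to 45 per arm the loss is 6 to 7 points for aPWV, 4 to 5 for LVMI and about 4 for T50. At the 10% attrition of the investigator's earlier 6-month trial (Preliminary Data, a), 54 × 0.90 = 48.6. With 48 to 49 per arm, power is 84% for aPWV, 90% for LVMI and 92–93% for T50.

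**Step 3: FMD.** d = 1.5/0.8 = 1.875; power stays above 99% at n = 45 on the plan's inputs.

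**Step 4: the per-protocol figure.** This set also excludes rescued participants. Starting from 46 completers, aPWV power is 80.9% after one rescue exclusion per arm (45), 80.0% after two (44) and 78.9% after three (43). The number of exclusions is assumed; the documents give no rescue rate.

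**Step 5: what ANCOVA could recover.** With equal variances at baseline and month 12 and correlation r between them, ANCOVA residual variance divided by change-score variance is σ²(1 − r²) / [2σ²(1 − r)] = (1 + r)/2. With df = 2n − 3, power returns to the n = 54 t-test figure at r of about 0.70 (n = 46) or 0.66 (n = 45) for all three outcomes. Below that r, ANCOVA more than recovers the loss: at r = 0.5 and n = 46, aPWV power is 92%. Above it, recovery is partial: at r = 0.9 and n = 46, aPWV power is 84%.

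**Step 6: the aPWV SD.** Section 10 also reports "In previous studies of CKD patients with comparable kidney function, the mean (SD) increase in aPWV was" 1.1 ± 1 m/s. At an SD of 1.0, aPWV power is 99% even at n = 45 and the loss is immaterial. The plan chose 1.5 for its calculation, and that value is used above.

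**The case against.** The strongest reply is that little is hidden. FMD and aPWV are the primary outcomes, and section 10 prints power for both at 45 per arm. Its 80% for aPWV is slightly below the recomputed 80.9%. This stands, and it is why the point is minor. It does not supply figures for LVMI or T50, and it does not make the 88% a complete-data figure under 15% loss.

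A second reply is that ANCOVA may be efficient enough to cancel the loss. It may (step 5), so a net shortfall for the ANCOVA itself is not shown. But the plan states t-test power, gives no correlation and claims no such gain.

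A third reply is that imputation would justify 54 per arm. Section 11 names the complete-data analysis as primary. Even if imputation were primary, it would not restore 54 observed values. LVMI is measured only at baseline and end of study (section 8), so there is no interim scan to draw on.

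Three stronger readings are tempting, and the documents do not support them.

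- **The trial is underpowered.** On the plan's inputs no complete-data power falls below 80%.
- **No primary method is named.** One is; only the role of imputation is loosely worded.
- **The per-protocol n of 45 is mislabelled and is really the ITT set.** Attrition is undefined. Section 7 has visits continuing after study drug is stopped, so a participant off drug may still give a month-12 value. Also, 46 completers less one rescue exclusion per arm is exactly 45, and section 4 calls a fall in bicarbonate unlikely. The label is defensible.

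**Conclusion.** The point holds as a minor error of statement. On the plan's t-test basis, 88%, 93% and 95% are no-loss powers. Under the plan's 15% attrition the complete-data ITT analysis has about 82% for aPWV, 89% for LVMI and 91% for T50 at 46 per arm (81%, 88% and 91% at 45).

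This rests on three assumptions: all of the 15% lack a month-12 value, the SDs are as the plan gives them, and the t-test stands in for the ANCOVA. If some of the 15% still attend month 12, power lies between these figures and the stated ones. The monitoring plan's remark that the study is not firmly confirmatory lowers the stakes further, although formal significance thresholds are set.

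**What to change.** 1. **Section 10.** State the power of the complete-data ITT analysis under 15% attrition, with the assumption that all of it means no month-12 value: 46 per arm, aPWV about 82%, LVMI about 89%, T50 about 91%. Keep the n = 54 figures only as the no-loss upper bound. Note that power lies between the two if some still attend (50 per arm: 85%, 91%, 93%).
2. **Section 11.** Keep complete-data ANCOVA as primary, and say that multiple imputation, the mixed model and the pattern-mixture model are sensitivity analyses.
3. **Section 10, Aim 1.** Leave the per-protocol label on n = 45. Add that this number must cover both attrition and rescue exclusions; one or two exclusions per arm from 46 completers still gives about 80–81% for aPWV.

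The cost is a few sentences and slightly lower stated powers. No participants, visits or analyses are added.

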  - 1 month: 1) remote or in-person safety visit (basic chemistry panel, adverse event assessment, gastrointestinal (GI) symptoms questionnaire, BP, pill compliance); 2) optional outcome measures: FMDBA, plasma AII, aldosterone, ET-1, and serum T50. Of note, aPWV will not be measured at 1 month as it is unlikely to change after only 4 weeks of treatment.
  - 3, 6 and 9 months: safety visit (basic chemistry panel, adverse event assessment, GI symptoms questionnaire, BP, pill compliance).
  - 6 months: in addition to the safety visit, outcome measures: FMDBA, aPWV, plasma AII, aldosterone, ET-1 and serum T50 and 24-hour urine collection.

- 12 months: 1) Adverse event assessment, GI symptoms questionnaire, BP, pill compliance; 2) outcome measures: FMDBA, aPWV, LVMI, serum basic chemistry panel, plasma AlI, aldosterone, ET-1, serum T50, venous blood gas, and 24-hour urine collection.

**4. Study Drug Dosing.** The study drugs (bicarbonate and the matched placebo) will be prepared by Belmar Pharmacy and will be identical in size, color, shape and taste. Each sodium bicarbonate capsule contains 7.7 mEq of bicarbonate and 178 mg of sodium. The matching placebo capsule will contain cornstarch. Belmar Pharmacy will bottle the capsules and label the bottles with code numbers to maintain the study's double blind and ship the bottles directly to the investigative site.

**a) Sodium bicarbonate:** Subjects randomly assigned to sodium bicarbonate therapy will receive 0.5 mEq/kg-lean body weight (LBW)/day for the entire 12 months. Participants will take ½ the daily dose in the morning and the other ½ in the evening. The number of capsules will be rounded to the nearest whole capsule. To reduce pill burden and increase compliance the maximum number of pills per day will be six.

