## 7. Safety monitoring

**• Expected adverse events:** Sodium bicarbonate therapy may cause bloating, flatulence and abdominal discomfort. Although previous studies using similar doses of sodium bicarbonate have not reported significant changes in edema, body weight or BP, sodium bicarbonate may cause edema to develop or worsen thereby increasing BP. Previous studies suggest fluid retention is greater when sodium is accompanied by the chloride anion rather than the bicarbonate anion. As shown in our **preliminary data**, sodium bicarbonate did

not result in increased BP. Sodium bicarbonate also has the potential for causing metabolic alkalosis and hypokalemia if it is retained rather than excreted in the urine. These expected adverse events will be monitored during the course of the study and in general, can be medically managed by adjusting antihypertensive and/or diuretic agents, providing potassium replacement and by dietary changes. Of note, none of these adverse events were observed in our short-term pilot study.

- **Dose reduction and discontinuation:**

- Serum bicarbonate >28 mEq/L: The intervention dose (study drug) will be reduced by 50% by the PI and diuretics will be adjusted as appropriate by the primary nephrologist or PCP. The PI will contact the primary nephrologist or PCP by phone or email and discuss changes in diuretics. The participant will return for a visit one week later to have serum chemistries rechecked. If the bicarbonate remains >28 mEq/L the intervention will be stopped by the PI and the participant will have serum bicarbonate measured weekly until it is <28 mEq/L. Plasma ionized calcium will be checked if bicarbonate is >30 mEq/L at any visit since an increase in pH can decrease the ionized calcium concentration. Management of low ionized calcium will be at the discretion of the PI based on symptoms reported by the patient. The PI will contact the primary nephrologist or PCP if she believes calcium supplementation is necessary and the primary physician will order the medication.

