## 8. Data Collection

- Demographics, medical history and physical examination will be performed at screening and baseline visit.
- Circulating measures: Subjects will report fasted for standard blood chemistry analysis at baseline, 1, 3, 6, 9 months and end of study. A venous blood gas (for pH and  $P_{CO_2}$ ) will be obtained at baseline and end of study to get a more complete description of the acid-base status of the participant. To assess participant's positive acid balance we will collect 24-hour urines at baseline, 6 months and end of study to measure net acid excretion and net endogenous acid production. A urine pregnancy test will be performed if clinically indicated at the screening visit.
- Outcome measures: FMDBA will be performed at baseline, 1 month (optional), 6 months and end of study. Aortic PWV will be performed at baseline, 6 months and end of study. LVMI will be performed at baseline and end of study. Plasma will be collected for measurement of AII, aldosterone and ET-1 and serum will be collected for measurement of  $T_{50}$ , at baseline, 1 month (if patient has in-person visit), 6 months and end of study.

- Other circulating markers of calcification: In addition, will measure serum fetuin-A (inhibitor of VC); serum calcium (promoter of VC); serum phosphate (promoter of VC); inflammatory markers (promoters of VC): serum C-reactive protein and cytokine 12 panel (IL-2, IL-4, IL-5, IL-6, IL-8, IL-10, IL-13, Interferon gamma, Interleukin 2 Receptor, Interleukin 1 beta, tumor necrosis factor); and markers of bone metabolism (serum parathyroid hormone, bone alkaline phosphatase, beta C-terminal telopeptide). These markers will be measured at baseline, 6 months and end of study.
- Resting BP: Arterial BP will be measured in triplicate while seated at rest using an automated oscillometric machine (Dinamap) at all in person study visits.
- Measures of adherence and safety:
  - Pill counts will be assessed at the quarterly visits and end of study to document subject adherence.
  - A GI symptoms questionnaire will be performed to assess tolerability of the intervention monthly (either via telephone or at an in person visit). Participants will be asked to rate symptoms of nausea, bloating, and diarrhea.
  - Adverse event assessment will be performed monthly either via telephone or at an in person visit. Additional telephone calls and PRN follow-up visits will occur at the discretion of the PI.

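### The primary analysis is labelled ITT but defined as ANCOVA on complete data, the role of multiple imputation is not stated, and observed month-6 values of patients lost later appear to go unused

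*Combined protocol and SAP*

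**What the plan says.** Section 11, General consideration, makes three statements in a row:

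- On the principle behind the main comparison, it states: "The primary analysis will be conducted on ITT basis".
- On the method and the patients it covers, it states: "Analysis of covariance (ANCOVA) with complete data will be the primary analysis for efficacy".
- On patients without a final value, it states: "Multiple imputation will apply because of missing data and sensitivity analysis will be conducted in various ways, including linear mixed effects model", with a pattern-mixture approach named as well.

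The plan for Aim 1 tests the change from baseline to month 12 in FMD and aPWV by ANCOVA at 0.025. It adds "longitudinal data analysis with mixed effect models", with group differences at each time point. Aims 2 and 3 use ANCOVA on the 12-month change at 0.05.

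Most outcomes have an intermediate value. Section 8 says "Aortic PWV will be performed at baseline, 6 months and end of study". FMD, the three hormones and T50 are also scheduled at month 6, and month 1 is optional. LVMI is measured only at baseline and at the end.

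Section 7 sets rules for stopping study drug, for example "If the bicarbonate remains >28 mEq/L the intervention will be stopped by the PI", with similar rules for blood pressure, potassium and edema. (The Data and Safety Monitoring Plan repeats the bicarbonate rule with a different threshold. The two passages must be reconciled, but that is a separate matter.) Neither section says whether the month-6 and month-12 outcome measures are still taken once drug is stopped.

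**The concern.** An analysis of patients with complete data is not an analysis of all randomised patients, so the first two statements conflict. The third does not settle the conflict. If imputation feeds the primary ANCOVA, the complete-data wording is wrong. If it does not, the primary analysis is of completers only. Its role, model and variables are not given, and nothing says that month-6 values enter it. Which result is the headline could therefore be settled after the data are seen.

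On the completer reading, a patient measured at month 6 and lost before month 12 contributes nothing to the primary test. If patients who are doing badly at month 6 leave one arm more readily than the other, those who remain are no longer comparable. The ANCOVA adjusts for baseline but not for what was seen at month 6, so it can create or hide an effect.

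**Working it through.** **1. What ITT was meant to cover.** Inputs for aPWV from section 10: difference 1.0 m/s, SD 1.5 m/s, two-sided 0.025, two-sample t-test.

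- 54 per arm: noncentrality 1.0 / (1.5 × √(2/54)) = 3.46, power 88.1% (plan: 88%).
- 45 per arm: 1.0 / (1.5 × √(2/45)) = 3.16, power 80.9% (plan: 80%).

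Both figures reproduce. The ITT figure uses all 54 per arm, and the 15% attrition is applied only to the per-protocol set. So ITT was counted as everyone randomised. A complete-data analysis at 15% loss has 54 × 0.85 = 45.9 per arm, where the same test has about 81–82% power. Label, method and power basis do not describe one analysis set.

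**2. When a completer ANCOVA is biased.** In one arm, let *p* be the fraction lost and *D* the mean month-6 change of those lost minus the arm mean. The month-6 change of those who stay is shifted by −*D* × *p*/(1−*p*). A slope *b* carries this to the baseline-adjusted month-12 value. The bias is *b* times the difference between the arms' shifts. It is zero if *D* = 0 in both arms, whatever the loss rates, and zero if the shifts are equal.

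Assumptions not in the documents: three visits with equal correlation ρ of 0.5, 0.7 or 0.8, and loss of the patients with the highest score, where score = month-6 aPWV change + noise of SD 0.75. With SD of change 1.5:

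- *b* = ρ(1−ρ) / [2(1−ρ)] = ρ/2, that is 0.25, 0.35 or 0.40.
- Correlation of score with change: 1.5/√(1.5² + 0.75²) = 0.894, so *D* = 1.5 × 0.894 × *i*(*p*). Here *i*(*p*) is the mean of the upper tail of a standard normal: 1.755 at 10%, 1.554 at 15%, 1.400 at 20%.
- Size of shift: 0.262 m/s at 10%, 0.368 at 15%, 0.470 at 20%.

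The simulation used 400,000 per arm and a true effect of 1.0 m/s, half of it present at month 6. Size of bias in m/s:

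| Loss mechanism | Formula, ρ = 0.5 / 0.7 / 0.8 | Completer ANCOVA, simulated | Likelihood estimate using month 6 |
|---|---|---|---|
| Random, 10% vs 20% | 0 | 0.00 | 0.00 |
| Baseline-driven, 10% vs 20% | 0 | 0.00 | 0.00 |
| Month-6 worsening, 15% in both | 0 | 0.00 | 0.00 |
| Month-6 worsening, 20% vs 10% | 0.052 / 0.073 / 0.083 | 0.05–0.09 | about 0.00 |
| Month-6 worsening in one arm (20%), random 10% in the other | 0.117 / 0.164 / 0.188 | 0.12–0.19 | about 0.00 |
| Worst leave one arm, best leave the other, 15% each | 0.184 / 0.258 / 0.294 | 0.20–0.31 | about 0.00 |
| Unseen month-12 value, 20% vs 10% | not applicable | 0.16–0.19 | 0.15–0.16 |

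The sign depends on which arm loses the patients.

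**3. Milder selection.** Suppose the odds of loss rise by a factor OR per SD of month-6 worsening, in one arm only. To first order the shift is *p* × ln(OR) × 1.5. At 15% and OR 1.5 this is 0.15 × 0.405 × 1.5 = 0.091 m/s. At 20% and OR 2 it is 0.20 × 0.693 × 1.5 = 0.208 m/s. With a correlation of 0.6–0.7 between the month-6 and month-12 changes, and no baseline adjustment, the bias is 0.091 × 0.6 = 0.05 to 0.208 × 0.7 = 0.15 m/s. With the baseline-adjusted slopes of step 2 it is smaller: 0.091 × 0.25 = 0.02 to 0.208 × 0.40 = 0.08.

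**4. Type I error (nominal 2.5%).** With 54 per arm and ρ of 0.5–0.7, the month-6-driven cases of step 2 that produce bias gave 3.0% to 9.3%. As a check, a bias of 0.187 with SD 0.273 is 0.68 standard errors; P(Z > 2.24 − 0.68) + P(Z < −2.24 − 0.68) = 6.1%, against 5.8% simulated. Moderate one-arm selection (odds 1.5–2 per SD) gave 2.7% to 4.1%. The steepest one-arm case tried gave 0.30–0.36 m/s and 10–12%.

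**5. Precision.** At 15% random loss and ρ = 0.5 the SD of the estimate is 0.273 for completer ANCOVA and 0.271 with month 6 used, a gain of about 1%.

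**The case against.** Several points count against a stronger reading.

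- **Imputation is mentioned.** A reader might infer that the plan ignores missing data. It does not: imputation, a mixed model and a pattern-mixture model are all named. Completers-only is the natural reading of the primary analysis, not a certain one. What stands is that the imputation has no stated place or content.
- **Unequal dropout.** A reader might infer that more loss on active drug is enough to bias the result. It is not: random loss of 10% against 20% gives zero bias.
- **Stopping rules.** A reader might treat stopping study drug as leaving the trial. The rules stop drug only. Rechecks continue for bicarbonate, blood pressure and potassium, rescued patients stay in the ITT analysis, and the month-12 visit carries no on-drug condition. The triggers are not FMD or aPWV, although section 12 names systolic pressure as something that affects the vascular and LV outcomes. Arm-related, outcome-related loss is therefore plausible but nowhere shown, and continued outcome measurement is nowhere stated.
- **The mixed model is already planned.** It appears twice, so a disagreement with the ANCOVA would be visible. That is true, but the plan does not say which result would then prevail in favour of the wider data set.
- **The mixed model is no complete cure.** It leaves 0.15–0.16 m/s when loss depends on unseen month-12 values. It adds nothing for LVMI, or from aPWV for patients lost before month 6. Imputation using month-6 values would serve as well, so the documents do not make the mixed model the only acceptable choice.

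**Conclusion.** The point holds as an unresolved conflict in section 11 between an ITT label, a complete-data definition and an imputation sentence without a role. On the natural reading, the primary test discards observed month-6 data. The resulting bias is conditional: it needs loss related to post-baseline outcome in a way that differs by arm.

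For aPWV the illustrative size is roughly 0.05–0.15 m/s with moderate selection, and less once baseline adjustment lowers the slope. It is about 0.3 m/s only with extreme selection. Against the 1.0 m/s target that is 5–15% and about 30%. Type I error is about 3–10%, slightly beyond that in the steepest case. These figures rest on assumed correlations, loss rates and mechanisms, none of which the documents supply. They show what is at stake and do not predict this trial's bias. FMD was not simulated.

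The change is worth making because the better analysis is already in the plan. The case rests on bias and on having one defined primary analysis, not on power.

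**What to change.** - Name one primary analysis of all randomised patients with any outcome data. Either (a) the planned mixed model, with baseline value, visit-by-arm terms and the month-12 contrast, or (b) ANCOVA after multiple imputation by arm, with month-6 values in the imputation model. Say which.
- Do the same for the hormones and T50.
- For LVMI, which has no month-6 scan, use imputation that includes month-6 aPWV and FMD.
- Keep complete-data ANCOVA as a sensitivity analysis. Keep the pattern-mixture analysis too, because neither primary option cures loss that depends on unseen month-12 values.
- State in the follow-up and safety sections that the month-6 and month-12 outcome measures are still collected after study drug is stopped.

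The cost is wording and slightly more model specification, since the mixed model and imputation are already mentioned in section 11. Almost no precision is gained.
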